### **8.4.2 Physical examination**

A complete physical examination should be performed at screening and EoT, including an evaluation of the head, eyes, ears, nose, throat, neck and lymph nodes, and the cardiovascular, dermatological, musculo-skeletal, respiratory, GI and neurological systems.

Before each Lutathera administration and at each visit during short and long-term follow-up (and at other visits if clinically indicated), a limited, symptom-directed physical examination should be performed at the discretion of the Investigator (see [Table 8-2](#)).

Documentation of all physical examinations must be included in the source documentation at the study site. Clinically relevant findings that are present prior to signing informed consent must be recorded on the appropriate eCRF that captures medical history. Significant findings made after signing informed consent which meet the definition of an Adverse Event must be recorded as an adverse event.

#### **8.4.3 Vital signs**

Vital signs include blood pressure, pulse rate and body temperature.

Blood pressure, pulse rate and body temperature will be assessed at screening, before each Lutathera administration, at EoT and at each visit during short and long-term follow-up (see [Table 8-2](#)). Blood pressure and pulse rate should be obtained in a quiet room at a comfortable temperature, with the patient's arm unconstrained by clothing or other material. Blood pressure and pulse rate measurements will be obtained after the patient has been in a sitting or supine position for at least 3 minutes, from the same arm (where possible), in the same position, with the same cuff size, using the same type of an automatic instrument with a digital readout, throughout the study. In addition, monitoring of vital signs (blood pressure and pulse rate) during the Lutathera and amino acid infusion is recommended.

Body temperature measurement can be either oral or tympanic; the method should be maintained throughout the study.

Significant findings that are present prior to baseline will be recorded in the medical history page, while changes during the study (including significant changes of the symptoms due to the underlying disease vs baseline) will be recorded on the Adverse Event page of the eCRF.

For patients enrolled in PPG cohort, additional measurements of blood pressure can be performed at Investigator discretion for the monitoring of hormone release symptoms (see [Section 4.5](#)). Such measurements will be recorded in eCRF as unscheduled visits.

#### **8.4.4 Height and Weight**

Height will be taken at screening, week 1 of cycle 4 treatment, EoT, last visit of short-term FUP, and every six months during long-term FUP.

Weight will be taken at screening, before each Lutathera administration, at the EoT, and every six months during long-term FUP. In addition, weight should be measured for each CrCl calculation (i.e. on the days when chemistry tests are taken).

Height will be obtained in centimeters (cm) and body weight in kilograms (kg) and rounded to the nearest 0.1 kg. Weight will be obtained in indoor clothing, without shoes.

#### **8.4.5 ECG**

Standard 12-lead ECGs will be performed at screening (baseline), immediately after each Lutathera/amino acid treatment procedure (following the completion of the amino acids infusion), and at the EoT visit ([Table 8-2](#)) to measure the ECG intervals (RR, PR, QRS, QT and QTcF).

ECGs will be performed in triplicate (at least 5 minutes apart) after the patient has been in a sitting or supine position for at least 10 minutes, and not immediately after a meal. The parameters will be measured as a mean value of minimally 3 beats; the mean of each parameter has to be used for CRF completion. The preferred sequence of cardiovascular data collection at the timepoints with multiple assessments is ECG collection first, followed by vital signs, and blood sampling.

Additional, unscheduled, safety ECGs may be repeated at the discretion of the investigator at any time during the study as clinically indicated. Unscheduled ECGs with clinically significant findings should be collected in triplicate.

The Investigator will note in the source documents (and in the eCRF) whether the ECG is normal or abnormal, as well as the clinical relevance of abnormal ECGs results and the different ECG intervals measurements, calculated using the mean value of 3 measurements for each parameter. Relevant ECG abnormalities at screening will be recorded in the medical history page, while changes during the study will be recorded on the Adverse Event page of the eCRF.

The original ECGs on non-heat-sensitive paper or a certified copy on non-heat sensitive paper, appropriately signed, must be collected and archived at the study site. Each ECG tracing should be labeled with the study number, subject initials (where regulations permit), subject number, subject date of birth, ECG date, and kept in the source documents at the study site.

#### **8.4.6      Laboratory evaluations**

The clinical laboratory assessments in this study include blood samples for hematology, blood chemistry, safety biomarkers, a urine sample for urinalysis, and a pregnancy test ([Table 8-2](#), [Table 8-4](#)).

Clinically significant abnormalities that are present prior to baseline will be recorded in the medical history page while any clinically relevant change from baseline onwards, will be recorded on the Adverse Event page of the e-CRF, possibly with a single diagnosis encompassing all changes possibly supporting to the single diagnosis.

In the event of a significant laboratory abnormality, or if clinical or laboratory evidence of toxicity occurs, the Investigator will collect additional specimens for repeat or additional analyses, at intervals appropriate to the abnormality. The patient will be closely followed until sufficient information is obtained to determine the cause or the value regresses. Appropriate remedial measures should be taken and the response recorded.

All previous safety laboratory results must be evaluated by the Investigator before each administration of Lutathera.

The list of laboratory parameters described in [Table 8-4](#) will be evaluated at the local laboratory of each site. Laboratory assessments will be performed according to the schedule in [Table 8-2](#).

The laboratory assessments after Lutathera doses (hematology, biochemistry and urinalysis, i.e. at Weeks 3, 5 and 7 of cycle 1 and 2 and at Weeks 5 and 7 of cycle 3 and 4) can be performed at another local laboratory outside of the Investigator site if considered necessary and convenient for the patient and investigator. In this case, the results and normal ranges should be provided for these tests and entered in eCRF as soon as possible to enable ongoing safety monitoring.

During the COVID-19 pandemic, the investigator should consider whether it is possible to arrange for the laboratory tests to be performed at a local laboratory for those patients who cannot come to the clinical site as scheduled. The investigator should collect and file all local lab reports in the patient medical record or chart.

**Table 8-4** **Laboratory assessments**

| Test Category   | Test Name  |
|-----------------|--|
| Hematology      | 

• WBC with differentials

• Platelets

• Hb

• MCV

• Haematocrit

  |
| Blood Chemistry | 

• BUN or urea

• Serum creatinine

• Creatinine Clearance

• Uric acid

• Albumin

• Total bilirubin

• AP

• AST/ASAT

• ALT/ALAT

• Gamma-GT

• Sodium

• Potassium

• Magnesium

• LDH

• Calcium

 |
| Urinalysis      | 

• Protein

• Blood

• Glucose

• Leucocytes

• pH

• UPCR

   |
| Pregnancy Test  | Serum / Urine pregnancy test   |

 Creatinine clearance must be calculated using the Cockcroft-Gault formula:  
*Est. Creatinine Clearance = [[140 - age (yr)]\*weight (kg)]/[72\*serum Cr(mg/dL)]*  
(multiply by 0.85 for women)  
Or  
*Est. Creatinine Clearance = [[140-age(yr)]\*weight (kg)]/[0.814\* serum Cr(µmol/L)]*  
(multiply by 0.85 for women)

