## **Clinical laboratory evaluations**

All laboratory data including safety biomarkers will be listed by participant, and visit/time and if normal ranges are available abnormalities will be flagged. Summary statistics will be provided by treatment and visit/time. Shift tables using the low/normal/high/ (low and high) classification will be used to compare baseline to the worst on-treatment value.

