#### **General analysis conventions**

**Pooling of centers:** Unless specified otherwise, data from all study centers will be pooled for the analysis. Due to expected small number of patients enrolled at each center, no center effect will be assessed.

**Qualitative data** (e.g., gender, race, etc.) will be summarized by means of contingency tables; a missing category will be included as applicable. Percentages will be calculated using the number of patients in the relevant population or subgroup as the denominator.

**Quantitative data** (e.g., age, body weight, etc.) will be summarized by appropriate descriptive statistics (i.e. mean, standard deviation, median, minimum, and maximum).

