### Unscheduled visits

In general, by-visit summaries will be presented by the scheduled visits (visit number and corresponding visit name of planned clinical encounter). Visit windowing will not be used for handling unscheduled visits. Instead, all unscheduled visits will be assigned a visit name of "Unscheduled". Such visits will be included in data listings and will contribute to the derivation of best- or worst-case values where required. Data from all assessments (scheduled and unscheduled), including multiple assessments, will be listed.

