## 2.6.4 Laboratory data

The routine laboratory tests are assessed locally at each investigational site. The summaries will include all on-treatment assessments available for the lab parameter collected no later than 56 days after the last study treatment administration date (see Section 2.1.1) as well as including all short-term and long-term assessments cumulatively in separate summaries.

The following summaries will be produced for hematology, biochemistry and urinalysis laboratory data as well as for safety biomarkers (by laboratory parameter):

- Worst on-treatment CTC grade (regardless of the baseline status). Each participant will be counted only for the worst grade observed on-treatment.
- Shift tables using CTC grades to compare baseline to the worst on-treatment value.
- For laboratory tests where CTC grades are not defined, shift tables using the low/normal/high/(low and high) classification to compare baseline to the worst on-treatment value.

These summaries will be repeated including the short-term and long-term follow-up periods, respectively.

The following listings will be produced for the laboratory data:

- Listings of all laboratory data, with CTC grades and classification relative to the laboratory normal range. Lab data collected during the short-term and long-term follow-up periods will be flagged.
- Listing of all CTC grade 3 or 4 laboratory toxicities

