## 2.6.5 Other safety data

### 2.6.5.1 ECG and cardiac imaging data

12-lead ECGs including PR, QRS, QT, QTcF, and RR intervals will be obtained for each participant during the study. ECGs are reviewed locally by each investigative site and assessed centrally.

The summaries will include all on-treatment assessments available no later than 56 days after the last study treatment administration date (see Section 2.1.1).

The following summaries will be presented:

- Change from baseline for ECG parameters by timepoint.
- Number and percentage of patients with on-treatment notable ECG values.
  - QT or QTcF
    - New value of > 450 and ≤ 480 ms
    - New value of > 480 and ≤ 500 ms
    - New value of > 500 ms
    - Increase from baseline of > 30 ms to ≤ 60 ms
    - Increase from baseline of > 60 ms
  - HR (=60/RR in seconds)
    - Increase from baseline >25% and to a new HR > 100 bpm
    - Decrease from baseline >25% and to a new HR < 50 bpm
  - PR
    - Increase from baseline >25% and to a new PR > 200 ms
    - New PR > 200 ms
  - QRS
    - Increase from baseline >25% and to a new QRS > 120 ms
    - New QRS > 120 ms

ECG parameters will be listed, and periods of assessment will be flagged.

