## 4 Change to protocol specified analyses

No change from protocol specified analysis was made.

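### SAP 2.6.4 does not carry over the by-visit laboratory summaries of Protocol 12.5.2; separately, growth can blunt a moderate renal decline in raw Cockcroft-Gault clearance for younger entrants

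*Protocol*

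**What the plan says.** **Clearance formula.** The footnote to Protocol Table 8-4 reads "Creatinine clearance must be calculated using the Cockcroft-Gault formula": (140 − age) × weight / (72 × serum creatinine in mg/dL), times 0.85 for females. It has no height or body-surface-area term. Protocol 8.4.4 adds that "weight should be measured for each CrCl calculation", so the weight is always the current one.

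**Protocol analysis.** Under clinical laboratory evaluations, Protocol 12.5.2 says "Summary statistics will be provided by treatment and visit/time", in addition to listings and shift tables. The opening of 12.5.2 confines safety summaries to the on-treatment period, which ends 56 days after the last dose. Baseline data are an exception, and so are long-term safety assessments, which are to be summarised separately in a form that is not specified.

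**SAP analysis.** SAP 2.6.4 names the worst CTC grade, "Shift tables using CTC grades to compare baseline to the worst on-treatment value", low/normal/high shifts where no grade exists, and listings. The grade and shift summaries are repeated with short- and long-term follow-up included. No by-visit laboratory statistic is named. SAP section 4 says "No change from protocol specified analysis was made".

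**General conventions.** SAP 2.1 says quantitative data "will be summarized by appropriate descriptive statistics", and SAP 2.1.1 says "In general, by-visit summaries will be presented by the scheduled visits". Neither says which parameters receive a by-visit table. The ECG section does name one: "Change from baseline for ECG parameters by timepoint".

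**The concern.** There are two separate points.

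The first is a mismatch between documents. The protocol promises by-visit laboratory statistics, the SAP does not name them, and the SAP says nothing has changed. Without them, the pooled output shows how bad a value became but not when, or whether it recovered.

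The second is how the clearance row behaves in growing patients. At unchanged creatinine, raw Cockcroft-Gault rises in proportion to weight. In a patient who enters at 12 and is followed until about 17.5, a moderate loss of function relative to body size may leave the raw value flat. A baseline-to-worst summary adds to this, because a growing patient's lowest raw clearance tends to occur early, when weight is lowest.

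The kidney is a principal risk organ (Protocol 4.3), and laboratory abnormalities over 5 years are a secondary endpoint. In the single-institution adult trial cited in 4.3, renal failure was rare (<1%) but began 3 to 36 months after treatment. The Amendment 02 rationale records that patients with prior nephrectomy are being treated.

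**Working it through.** The plan gives no figure for clearance over growth, so there is none to reproduce. Its two versions of the formula agree: 72/0.814 = 88.5, the µmol/L-per-mg/dL conversion.

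**Inputs from the documents.** Entry age is 12 to <18. Dose 4 comes 24 weeks after dose 1, and follow-up runs 5 years from the last dose, so the span is about 5.5 years. Weight is re-measured on each chemistry day.

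**Assumed inputs.** The documents give no age, weight or height distribution. All body sizes below are assumptions.

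**Rise in raw clearance at unchanged creatinine.** Multiplier = [(140 − age₂) × weight₂] / [(140 − age₁) × weight₁]; the factor 0.85 cancels.

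| Entrant (assumed weights, kg) | 5 years after last dose | Final weight ±10% | 36 months | About 3 months |
|---|---|---|---|---|
| Boy, 12 (42 to 65) | 122.5×65/(128×42) = 1.48 | 1.33 to 1.63 | 1.34 | 1.08 |
| Girl, 12 (43 to 56) | 122.5×56/(128×43) = 1.25 | 1.12 to 1.37 | 1.20 | 1.05 |
| Boy, 15 (56 to 70) | 119.5×70/(125×56) = 1.20 | 1.08 to 1.31 | 1.16 | 1.04 |
| Boy, 17 (65 to 71) | 117.5×71/(123×65) = 1.04 | 0.94 to 1.15 | 1.03 | 1.01 |

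Intermediate weights, in table order, are 58, 53, 67 and 69 kg at 36 months (age +3.5 years) and 45.5, 45.5, 58.5 and 66 kg at about 3 months (age +0.7 years).

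**Worked case, boy entering at 12.** Creatinine goes from 0.55 to 0.81 mg/dL and height from 150 to 175 cm.

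- Raw clearance at entry: 128×42/(72×0.55) = 136 mL/min.
- Raw clearance at 5 years: 122.5×65/(72×0.81) = 137 mL/min.
- Serum creatinine: 0.81/0.55 = 1.47, a rise of 47%.
- Height/creatinine: (175/150)×(0.55/0.81) = 0.79, a fall of 21%.

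The clearance row, and any baseline-to-worst comparison on it, would not register this change at year 5. The serum creatinine row would.

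**Same boy, creatinine rising from muscle growth alone.**

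- Creatinine +20%: raw clearance 1.48/1.2 = 1.23; height-based 1.167/1.2 = 0.97.
- Creatinine +40% (to 0.77 mg/dL): raw clearance 1.48/1.4 = 1.06; height-based 1.167/1.4 = 0.83.

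The raw rise is then 6% to 23% rather than 48%, and the height-based index falls 3% to 17% with no renal disease.

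**Second check, indexing to body surface area with other growth assumptions.** For entry at 12 with growth from 40 to 60 kg and 150 to 170 cm, the raw rise at unchanged creatinine is 44% (20% to 49% across four growth patterns). A flat raw value then corresponds to a 23% fall in indexed clearance (14% to 25%). A 40% indexed fall would still show as a raw fall of 22% (20% to 30%). For entry at 17, a flat raw value hides 0% to 3%.

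**Documents side by side.** Protocol 12.5.2 commits to by-visit laboratory statistics. SAP 2.6.4 lists its laboratory summaries and includes none. The SAP 2.1 conventions govern format and layout and commit no laboratory parameter to a by-visit table. This point needs no assumption.

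**The case against.** The strongest reply has four parts.

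1. *The 5-year by-visit table is not an existing promise.* A reader might infer that it is. The documents do not support that: 12.5.2 limits its summaries to the on-treatment period and says only that long-term assessments are summarised separately. The clear promise covers the period when growth bias is small (about 1% to 8%). This stands.

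2. *Renal decline is not invisible.* A reader might also infer that it is. Serum creatinine has its own worst-value and shift summaries, repeated through long-term follow-up, and every value is listed. With 11 patients enrolled at Amendment 03, the listings can be read one by one. Related nephrotoxicity is reportable as an AESI in follow-up. This stands in large part. The limits are that follow-up recording is restricted to related SAEs and AESIs (plus all secondary malignancies), that the AESI description itself refers to measured or estimated clearance, and that listings are not a pooled time course.

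3. *The worked case is close to normal growth.* A fall of 21% in the height-based index is near the 17% that muscle growth alone could produce. This stands. The index is supportive and cannot by itself separate disease from growth.

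4. *By-visit tables do not cure the growth effect.* A by-visit table of raw clearance carries the same bias. This also stands, and it is why the two points need separate remedies.

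**Conclusion.** Both points hold, and both are minor. SAP 2.6.4 departs from Protocol 12.5.2 by not naming by-visit laboratory summaries, clearly so for the on-treatment period, and SAP section 4 does not declare it.

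Separately, unindexed clearance with current weight can partly or fully offset a moderate size-adjusted decline over long-term follow-up in patients entering at about 12 to 15. At unchanged creatinine the central estimates of the 5-year rise are roughly 20% to 50% for entry at 12, about 20% for entry at 15 and a few percent for entry at 17. These rest wholly on assumed growth, and they shrink if creatinine rises with muscle mass. Large declines are blunted rather than hidden.

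Nothing here supports a claim that dosing is biased: growth during the roughly 24 weeks between first and last dose is small, and Table 6-4 has its own creatinine criterion. The co-primary endpoints, which are organ dose and first-cycle safety, are unaffected.

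**What to change.** Amend SAP 2.6.4 as follows.

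1. Restore the by-visit laboratory summaries for the on-treatment period, or record their omission in SAP section 4. As an improvement rather than an existing promise, extend them to short- and long-term follow-up, with percent change from baseline for serum creatinine and creatinine clearance.
2. Beside these, not in place of them, show one pre-specified height-based eGFR (constant × height / creatinine) as a supportive descriptive row. Use the same formula throughout, including after age 18, so that the constant cancels in percent change, and use the last measured height. Add a note that normal muscle growth can itself give a modest apparent decline, and read the row together with creatinine, raw clearance and urine protein where collected.

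Table 6-4 stays as it is.

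The cost is one by-visit table and one derived variable. No new procedure is needed: height is measured every six months in long-term follow-up (Protocol 8.4.4), and chemistry is drawn at those visits (Protocol 4.3). The downsides are carried-forward height at some treatment and early follow-up visits, and the limited specificity of the height-based row.

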#### 8.4.7 Urinalysis

A midstream, clean-catch urine specimen will be collected for dipstick analysis of protein, blood, glucose, leucocytes and pH, according to the schedule in [Table 8-2](#). If the dipstick result is 2+ or greater for blood, protein or leukocytes, microscopy needs to be performed. If there is an explanation for the positive dipstick result, e.g., menses, it should be recorded, and there is no need to perform microscopy. A spot urine sample should also be collected before each Lutathera infusion and also 3 weeks after each Lutathera infusion for UPCR test ([Table 8-2](#)).

#### **8.4.8 Pregnancy Test**

All menarchal girls and their parents/caregivers should be informed about the potential risks of pregnancy and the need to prevent pregnancy during the study. It is important to be sensitive in introducing this issue, as understanding and comprehension of puberty, sexual activity, pregnancy and contraception is influenced by age, as well as factors such as precocity, socio(educational) economic and familial background. These discussions with the patient and her parents/caregivers are therefore best performed by investigators familiar with the pediatric subject and her family and should be guided by requirements of the local regulatory authorities. These discussions should take into account the socio-economic, cultural factors and religious beliefs of the adolescent participant and her family. The investigator should also discuss the management of the pregnancy test results with the patient and her parents/caregivers. The privacy of the patient should be considered in accordance with the local law and ethics.

All female patients should not procreate until seven months after the last Lutathera dose (see [Appendix 1](#) for contraception measures).

A pregnancy test must be performed at screening and prior to each Lutathera treatment (within 2 weeks) for every female patient of childbearing potential. This should be continued during treatment and for 7 months after ending treatment. The pregnancy test must be performed as per schedule described in [Table 8-2](#). During this period, monthly pregnancy serum tests can be changed to urine tests if there is no personal visits. The urine pregnancy testing should use a laboratory-based urine assay or a commercially available kit.

If preferred by the patient, the urine pregnancy tests can be done at the clinical site. In case the urine pregnancy test is positive, the patient must contact the investigator immediately. A positive urine test needs to be confirmed with blood test. If the confirmatory blood pregnancy test is positive during treatment period, the participant must be discontinued from study treatment.

Females of child-bearing potential are defined as all females physiologically capable of becoming pregnant. This includes female pediatric patients who are menarchal or who become menarchal during the study.

Additional pregnancy tests may be performed at the investigator's discretion during the study.

Patients becoming pregnant must be discontinued from study drug. For requirements on pregnancy reporting see [Section 10.1.7](#).

